11.3.4 Subject withdrawal

Subjects are free to discontinue participation in the clinical investigation at any time, without prejudice to further treatment. Subjects who discontinue the clinical investigation should always be asked about the reason(s) for their discontinuation and about the presence of any AEs or ADEs and, if possible, be assessed by the investigator.

Subjects may be withdrawn from investigation treatment and assessments at any time, if deemed necessary by the principal investigator or sponsor.

In case of withdrawal of consent or withdrawal of the subject from the clinical investigation, AEs will be followed up by the investigator according to Section 12.5.

Subjects who are prematurely withdrawn from the study and have received at least 1 study treatment will be asked to undergo a final examination to monitor the subject's safety and document any AEs.

Subjects may be discontinued for the following reasons:

- Subject's request;
- Ineligibility including the development of any undercurrent illness(es), infections or condition(s) before treatment that might interfere with the subject's participation in the clinical investigation;
- AE(s), which in the opinion of the investigator may jeopardize the subject's health or compromise the study objectives (a corresponding AE pCRF page must always be completed);
- Poor compliance and/or disregarding the investigator's instructions;
- Major CIP violation;
- Any problem (not covered by the other categories) deemed by the investigator and/or the sponsor to be sufficient to cause discontinuation.

Every effort should be made to follow-up all subjects in accordance with this CIP. Prior to withdrawal for loss to follow-up, the investigator will try to contact the subject on 3 separate occasions and document each attempt in the subject medical records.

In case of early withdrawal, reasons, circumstances and findings should be fully described on the End of Study page in the pCRF respecting the subject's rights.

11.3.5 Subject enrollment, number, and duration of subject's participation

Subjects who have signed the ICF will be considered enrolled. Enrolled subjects who have completed the 4-week screening phase and comply with respective eligibility criteria, will be randomized.

Randomized subjects will undergo a 6-week treatment period including 6 weekly treatments with the Chordate System S211 and a subsequent 4-week follow-up period.

Approximately 148 subjects will be randomized to achieve 132 evaluable subjects (see sample size calculation Section 13.5). A group-sequential design with one interim analysis after approximately 50 subjects have completed the 6-week treatment period will be used. It will allow the premature termination of the study due to efficacy or futility or adaption of the sample size. If during the conduct of the study the drop-out rate proves to be higher than expected (>10%), enrollment will continue until at least 132 subjects were assessed for the primary endpoint.

11.4 Procedures and assessments

11.4.1 Diary

Subjects will be instructed to complete a paper diary each day from screening up to the follow-up visit. The following information will be recorded:

- Use and changes of concomitant medication (type, dose and dosing schedule);
- AEs;
- Headache and migraine days.

11.4.2 Questionnaires

During the study subjects will be asked to complete 2 self-administered questionnaires.

11.4.2.1 Headache impact test

The HIT-6 is a 6-item questionnaire that evaluates the extent of disability a subject experiences due to headache by measuring the subject's level of pain, social functioning, role functioning, vitality, cognitive functioning, and psychological distress.

11.4.2.2 MSQ

The MSQ is a 14-item, self-administered questionnaire that assesses the impact of migraine on health-related quality of life during the past 4 weeks. It includes 3 dimensions: role function-restrictive, role function-preventive, and emotional function.

11.4.3 Patient global impression of severity

The PGI-S is a 1-item questionnaire to assess the subject's impression of disease severity. The subjects will rate the severity of their condition on a scale from 1 to 4:

- 1: normal
- 2: mild
- 3: moderate
- 4: severe

11.4.4 Physical examination

A complete physical examination will be performed at screening including the following organs/body systems: general condition; skin; ears/nose/throat; head/thyroid; cardiovascular; respiratory; gastrointestinal; lymphatic; musculoskeletal; neurological; genitourinary; endocrine; others (e.g. allergies). Abnormalities will be recorded in the source data and transferred in the pCRF.

11.4.5 Other assessments

- **Demography:** age, sex, race, height, weight, body mass index.
- **Medical and surgical history:** from subject interview and medical records covering relevant past medical history. Presence of allergies and pronounced septal deviation will be recorded separately.

The following information will be documented separately in regard to migraine history:

- Migraine onset;
 - Average headache days per month;
 - Average migraine days per month;
- **Concomitant medications** will be recorded in the pCRF. Variables are as follows: type of medication; route; dose; unit; regimen; start date; end date (with a yes/no question for 'ongoing'); reason taken.
 - **Urine pregnancy test:** urine pregnancy tests will be performed in women of childbearing potential at the times specified in the schedule of assessments (Section 3).

11.4.6 Factors that may compromise the outcome

Specific subject characteristics have been included with the aim of reducing variables that could influence treatment outcomes and interpretation of these. The rationale for individual subject characteristics to be included in the clinical investigation is detailed below.

- Diagnosis of chronic migraine with or without aura according to IHS classification (ICHD-III Beta): this is a chronic migraine study and it is important to ensure that only subjects with the target indication are enrolled.
- Male or female: although females experience more migraines than males, it is important to study outcomes in both genders.
- Age 18 to 65 years: this clinical investigation is an adult migraine study. Age above 65 years is associated with higher comorbidity and concomitant medications, which can confound interpretation of treatment effects.
- Age of migraine onset before 60 years: late onset of migraine is very rare and often mimics other diseases. Treatment response in these subjects may be atypical and confound results.
- History of migraine for at least one year: this is required in order to diagnose migraine more accurately. The migraine does not need to be in its chronic form for the complete year; however, to meet the criteria for chronic migraine (see first bullet point), subjects must have ≥ 15 headache days per month (of which at least 8 days fulfill the IHS criteria for migraine) for more than 3 months before screening.

11.4.7 Appropriateness of measurements

The use of simple subject diaries to record migraine details is recommended by the IHS and necessary to gather treatment outcome data.

Migraine pain and associated symptoms impact on subjects' daily functioning and quality of life. The performance endpoints, and associated variables and measurements, are consequently subject self-reported and reflect these elements.

The HIT-6 and MSQ are well-established measures for the evaluation of headache-related disability in migraine patients. The PGI-S is a widely used instrument determining the subject's impression of disease severity.

A combination of AE review and ad hoc subject AE reporting (via the diary) should ensure an accurate representation of AEs occurring during the clinical investigation.

11.5 Schedule of the clinical investigation

The schedule of assessments is provided in Section 3.

11.5.1 Screening

After written informed consent is obtained, the following assessments will be performed and information will be recorded in the pCRF:

- Check of inclusion and exclusion criteria;
- Documentation of demographics and medical and surgical history;
- Physical examination;
- Documentation of prior and concomitant medication;
- Urine pregnancy test in women of childbearing potential;
- Completion of questionnaires (HIT-6, MSQ);
- Assessment of PGI-S.

A paper diary will be handed out to the subjects to be completed during the 28-day screening phase.

Where a subject fails to fulfill the inclusion and exclusion criteria, this will be documented and the signed consent form retained by the principal investigator. The subject will not be advanced any further into this clinical investigation and an End of Study pCRF page will be completed.

11.5.2 Treatment

Visit 1 (Day 0)

Prior to any study related assessment the investigator will do a SARS-CoV-2 test, if required by site policy. If the test result is positive the patient will be asked to take the measures, which the authorities require in this case. The patient may come back to the site and continue the study after these requirements are fulfilled and a negative test result is present.

Afterwards the investigator will discuss with the subject any changes in their health during the screening phase and any changes in their medication or any new concomitant medication they may have used. The investigator will also review the subject's paper diary entries and ensure that the diary has been completed accurately. Additionally, the following assessments will be performed:

- Completion of questionnaires (HIT-6, MSQ);
- Assessment of PGI-S.

Subjects who continue to meet all inclusion criteria and none of the exclusion criteria will be randomized to 1 of the 2 study treatments.

Randomized subjects will be treated as described in Section 11.2.1 and detailed in the IFU. Any AEs or device defects occurring during or after treatment will be documented in the pCRF.

Visits 2, 3, 4, 5, and 6 (Day 7, 14, 21, 28, and 35 [± 3 days each])

At each visit, subjects will receive study treatment as described in Section 11.2.1 and detailed in the IFU.

At Visit 3 additionally the following assessments will be performed:

- Completion of questionnaires (HIT-6, MSQ);
- Assessment of PGI-S.

The subjects will be asked about any AEs and changes in concomitant medication since the last visit and any new or changed information will be documented in the pCRF.

Visit 7 (Day 42 ± 3 days)

The following assessments will be performed:

- Documentation of AEs;
- Documentation of changes in concomitant medication;
- Completion of questionnaires (HIT-6, MSQ);
- Assessment of PGI-S.

11.5.3 Follow-up (Day 70 ± 3 days)

Five weeks after the last study treatment, subjects will be asked to return to the site. The following assessments will be performed:

- Urine pregnancy test in women of childbearing potential;
- Documentation of AEs;
- Documentation of changes in concomitant medication;
- Completion of questionnaires (HIT-6, MSQ);
- Assessment of PGI-S.

The investigator will complete the End of Study page in the pCRF.

11.5.4 Early termination

In case a subject prematurely discontinues the clinical investigation (for reasons see Section 11.3.4), the End of Study page in the pCRF will be completed.

In case of early withdrawal, reasons, circumstances and findings should be fully described on the End of Study page in the pCRF respecting the subject's rights.

11.5.5 Medical care upon termination of the clinical investigation

After the final visit subjects will not receive any further study-specific treatment. They will be treated according to the investigator's discretion.

11.6 Clinical monitoring

The monitor will be responsible for ensuring that the investigators are aware of their responsibilities and for securing investigator compliance with the CIP, the signed agreement, EN ISO 14155:2020 and any conditions of approval imposed by the reviewing ethics committee (EC), component authority (CA) and/or local institution. During the clinical investigation, the monitor will have regular contacts with the investigation site. These contacts will include visits by the monitor to confirm that the facilities remain adequate to specified standards and that the investigation team is carrying out the procedures stated in the CIP. All data must be accurately recorded in the pCRF and source data verification will be performed by the monitor, to verify clinical investigation compliance and the accuracy of recorded data. The investigator must permit the monitor to visit the site at regular intervals and the pCRFs and other records must be accessible during the visits. The planned extent of source data verification (SDV) is detailed in the monitoring plan. The monitor or other sponsor personnel will be available between visits if the investigator or other staff at the site needs information and/or advice.

Authorized representatives of the sponsor and/or regulatory agencies may visit the site to perform audits/inspections, including SDV. The investigator will permit authorized inspectors

to inspect all facilities and records relating to the clinical investigation and aid the inspector to perform the audit in a timely fashion. It is the joint responsibility of both the sponsor and the investigator to ensure that the clinical investigation has been conducted in line with all applicable regulations.

11.7 Training of staff

All study site personnel should be present at the site initiation visit, during which the sponsor and/or the contract research organization (CRO) who was trained in advance by the sponsor and acting on his behalf will provide documented training on use of the device, the pCRF and clinical investigation conduct. It is the responsibility of the investigator to train any member of the research team who was not present at the site initiation visit or joined the clinical investigation at a later date on the study procedures before undertaking any clinical investigation responsibilities.

A Study Personnel and Authorization Log will be completed to indicate which activities the investigator has authorized to be performed by each research team member. This must be updated before a new or existing team member undertakes any new responsibility.

The investigator will ensure that appropriate training relevant to the clinical investigation is given to the medical, nursing and other staff involved and that new relevant information for this clinical investigation is forwarded to the staff involved.

12 Adverse events, adverse device effects, and device deficiencies

12.1 Definitions of adverse events and adverse device effects

Adverse event

An AE is defined as any untoward medical occurrence, unintended disease or injury or any untoward clinical signs (including abnormal laboratory findings) in subjects, users or other persons. For subjects this definition includes events whether or not related to the investigational medical device or comparator and those events related to the procedures involved (any procedure in this CIP). For users or other persons this definition is restricted to events related to the investigational medical device.

The definition of AE in this study does not include adverse experiences observed by the patient or in the patient before the investigational medical device application. Those adverse experiences occurring after provision of informed consent and prior to application of the investigational medical device will be recorded as part of the medical history. However, if the condition deteriorates at any time from date of administration of the investigational medical device during the study it should be recorded and reported as an AE.

The definition of an AE in this study does not include anticipated device effects of mild character (sneezing, increased nasal secretion, increased tear secretion, paresthesia of the lip, Chordate Medical AB

slight pain, slight discomfort, mild burning sensation, minor epistaxis [at withdrawal of catheter]). A list of anticipated device effects is also provided in Section 8.1. However, increase in severity from mild of the anticipated device effects listed above will constitute an AE. Any hospitalization due to the above-mentioned conditions will constitute an SAE.

The definition of an AE in this study does also not include migraine-associated symptoms (nausea, photophobia, phonophobia and vomiting), clinical disability and headache if they remain within the same severity and frequency observed by the patient before the study device use. Any hospitalization due to the above-mentioned conditions will constitute a SAE.

Adverse device effect

An ADE is defined as an AE that is related to the use of the investigational medical device. This includes any AE resulting from insufficiencies or inadequacies in the instructions for use, the deployment, the implantation, the installation, the operation, or any malfunction of the investigational medical device. In addition, this includes any event that is a result of a use error or intentional misuse.

Serious adverse event

An SAE is defined as any adverse event that led to any of the following: (a) death, (b) serious deterioration in the health of the subject, that resulted in any of the following: (i) life-threatening illness or injury, (ii) permanent impairment of a body structure or a body function, (iii) hospitalization or prolongation of patient hospitalization, (iv) medical or surgical intervention to prevent life-threatening illness or injury or permanent impairment to a body structure or a body function, (v) chronic disease, (c) fetal distress, fetal death or a congenital physical or mental impairment or birth defect

Serious adverse device effect

An SADE is defined as an ADE that has resulted in any of the consequences characteristic of an SAE.

Unanticipated serious adverse device effect

An unanticipated SADE (USADE) is defined as an SADE which by its nature, incidence, severity or outcome has not been identified in the current version of the risk analysis report.

An anticipated serious adverse device effect (ASADE) is an effect which by nature, incidence, severity or outcome has been identified in the risk analysis report. There are no ASADES for this clinical investigation.

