11.2.5 Previous and concomitant medications and treatments

Subjects must be on a stable prophylactic migraine medication regimen, if any, during the 3 months prior to screening and maintain this regimen (no change in type, frequency or dose) from screening to end of follow-up. No new prophylactic migraine medication may be initiated. Treatment with Botox is not allowed during the study (from screening to end of follow-up).

Medication, which is considered necessary for the subject's safety and well-being, may be given at the discretion of the investigator at any time.

Subjects can use their regular acute migraine medication, when necessary, during the course of the clinical investigation. However, all such use and any changes must be documented in the diary by the subjects.

The diary will be used to collect data about the use of concomitant medication in combination with discussions with the subject and medical record review. The site will record all concomitant medications in the appropriate sections of the pCRF.

Subjects will not be included in the investigation if they have previously been implanted with a stimulator or any implantable device in the head and/or neck or a pacemaker/ defibrillator, or if they have previously undergone sinus surgery or received treatment with therapeutic x-ray intervention in the facial region.

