12.2 Reporting of adverse events

12.2.1 Methods for eliciting adverse events

All subjects will be carefully monitored for the occurrence of AEs during the clinical investigation period from first treatment to the completion of follow-up. At clinical

investigation visits, the investigators will collect AE information using non-leading questions such as “have you experienced any new health problems or worsening of existing conditions?”. Events directly observed or spontaneously volunteered by subjects will also be recorded. In addition, subjects will be asked to contact the investigator if they feel unwell at any time between treatment and the end of their study participation.

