All SAEs for which a **causal relationship** between the SAE and the investigational medical device, diagnostic or therapeutic procedures performed as part of the clinical trial or other conditions of the trial conduct **cannot be excluded and** which indicates an imminent risk of death, serious injury, or serious illness **and** that requires prompt remedial action for other patients/subjects, users or other persons or a new finding to it will be reported by the sponsor or sponsor's representative immediately, but no later than 2 calendar days from the sponsor's or sponsor's representative's awareness of the new reportable event or of new information in relation with the already reported event to the all national CAs where the clinical investigation is conducted.

Any other SAEs for which a **causal relationship** between the SAE and the investigational medical device, a comparator device, diagnostic or therapeutic procedures performed as part of the clinical trial or other conditions of the trial conduct **cannot be excluded** or a new finding to it will be reported by the sponsor or sponsor's representative immediately, but no later than 7 calendar days from sponsor's or sponsor's representative's awareness of the new reportable event or of new information in relation with the already reported event to all national CAs where the clinical investigation is being conducted.

SAE EMERGENCY CONTACT DETAILS

Medical Monitor: [REDACTED]

Phone: [REDACTED]

Email: [REDACTED]

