4.4 Safety Analysis

Safety variables will be analyzed based on the SAF.

Adverse events (AEs)

Adverse events will be coded by the Medical Dictionary for Regulatory Activities (MedDRA) version 21.0.

The analysis will be based on treatment emergent AEs (TEAEs), i.e. AEs which started after first treatment. Incidences of TEAEs will be summarized by preferred term (PT) and system organ class (SOC). TEAEs related to the medical device, TEAEs related to procedure, and serious TEAs will be tabulated separately. TEAEs will be summarized also by preferred term (PT), system organ class and intensity. Listings will be generated for TEAEs, serious TEAEs, TEAEs related to procedure or medical device and non-treatment emergent AEs.

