The listings are always sorted by treatment group, center, and subject. If a different sorting order should be used for some listings this will be remarked separately. The variables for the special listings are explicitly given in the description of listings. All listings will be presented for the safety analysis set, if not stated differently, and indicator variables for further analysis sets, e.g., full analysis set, will be added.

Screened but not treated subjects (e.g. withdrawal before treatment) will be considered in tables and listings describing disposition of subjects, analysis sets and discontinuation as well as listings for subject demographics and migraine history.

The following title will be used for all generated tables, listings, and graphs:

PM007 – Final Analysis

Page # of #

<Subtitle for description of contents - if applicable>

<Analysis set>

The numbering NNN of the tables/listings/graphs will be stated in the detailed description (Appendix A).

Following footnote will be used for all generated tables, listings, and graphs:

Date: <Actual date(ddmmmyyyy)>

Program: <Name of program>

The statistical evaluation will be performed using SAS version 9.4 or higher.

5 Changes from Protocol

- The wording “monthly headache days” was changed to “4-week headache days” in order to avoid confusion. The analysis is based on 4 week (28 day) assessment windows and not on calendar months (30 days).
- For PGI-S no Wilcoxon test for change from baseline will be performed, since this is a categorical parameter.
- Secondary efficacy outcomes will also be analyzed for the PP set.
- An additional unblinded subgroup analysis (the unblinded analysis of the German subjects) will be performed.
- No Van Elteren test will be used for primary performance endpoint if the data is not normally distributed as no adjustment of alpha is possible according to group-sequential design with O’Brien & Fleming alpha spending function. The ANCOVA will be used even if the normal distribution cannot be shown. Due to the large sample size, it can be assumed that the data are approximately normal distributed.

6 Literature

Bayliss, M. S., & Batenhorst, A. S. (2002). *The HIT-6 TM A User's Guide*. Research Triangle Park, NC: QualityMetric Incorporated, Lincoln, RI and GlaxoSmithKline.

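### Serious events between consent and first device use have no clear SAE status or 24-hour reporting duty, and the protocol contradicts itself on the point

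*Protocol*

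**What the plan says.** The operative rule appears in four places in the protocol.

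- Section 12.1 rules out earlier events with the words "AE in this study does not include adverse experiences observed by the patient or in the patient before the investigational medical device application". Its next sentence says that an event "occurring after provision of informed consent and prior to application of the investigational medical device will be recorded as part of the medical history".
- Footnote a to the schedule of assessments (Section 3) repeats this for any change in health before first treatment.
- Section 12.2.1 sets the AE monitoring period as "from first treatment to the completion of follow-up".
- Section 12.5 evaluates for AEs those subjects who have been exposed to the device.

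Other text points the other way.

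- The opening of 12.1 counts as AEs "those events related to the procedures involved (any procedure in this CIP"), with no start date.
- Section 12.4 requires the authorities to be told of SAEs that may be linked to "diagnostic or therapeutic procedures performed as part of the clinical trial or other conditions of the trial conduct".
- Section 11.4.1 has subjects keep the diary from screening and names AEs among its items, whereas the schedule starts diary AEs at Visit 1.
- SAP 4.4 plans listings that include "TEAEs related to procedure or medical device and non-treatment emergent AEs".

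Trial conditions already apply in screening. Under 11.3.5 a subject is enrolled on signing consent. Under 11.2.5 a subject on prophylaxis must "maintain this regimen (no change in type, frequency or dose) from screening to end of follow-up", and Botox is not allowed over the same period.

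**The concern.** A definition that excludes everything before first device use keeps the comparison between arms clean, which is reasonable for treatment-emergent tables. Here the same definition also decides what can be an SAE, and therefore what must be reported within 24 hours and assessed for causality. Subjects spend four weeks enrolled and under trial restrictions before that definition starts to apply to them.

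If a serious event occurs in that time and is linked to a trial procedure or to the conditions of participation, the text that would make it reportable and the text that removes it from the AE definition cannot both be followed. Sites could handle the same event differently. The trial's account of harm from taking part, as distinct from harm from the device, could then be incomplete.

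**Working it through.** The plan gives no figure to reproduce. The check follows the definitions and then takes three cases through the text.

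**The chain**

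1. An event before first device application is not an AE in this study (12.1, second paragraph; footnote a).
2. An SAE is an adverse event with one of the listed serious outcomes (12.1).
3. From 1 and 2, a serious event before first device application is not an SAE.
4. The 24-hour report (12.2.2, 12.4) and the assessment of seriousness, severity, causality and outcome (12.2.2, 12.3) attach to AEs and SAEs. Medical history (11.4.5) carries no such fields.

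**Three cases in screening**

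- *Serious event linked to a trial procedure, subject later treated.* The opening of 12.1 and the triggers in 12.4 say it is reportable. The second paragraph of 12.1, footnote a and 12.2.1 say it is medical history. If the condition worsens after first device use, 12.1 makes that worsening an AE, but not the screening event itself.
- *Hospitalization for headache or migraine symptoms.* A sentence in 12.1 makes hospitalization for these an SAE and gives no date. Its paragraph takes the state before device use as the reference, so its reach into screening is arguable.
- *Serious event in a subject never treated.* The worsening clause cannot apply, and 12.5 does not cover the subject. SAP 4.8 says: "Screened but not treated subjects (e.g. withdrawal before treatment) will be considered in tables and listings describing disposition of subjects", analysis sets and discontinuation, and in listings of demographics and migraine history. General medical history is not named, and other listings default to the safety set unless stated otherwise.

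**Two ways to read 12.1**

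- If the second paragraph narrows the opening, there is little contradiction within 12.1, but the gap is definite: no serious screening event is an SAE.
- If the opening governs procedure-related events, those are reportable, but 12.2.1, 12.5 and footnote a provide no collection for them. Serious events with another cause, or of unclear cause, stay outside.

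The text needs repair on either reading.

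**The SAP listing**

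SAP 4.4 defines treatment-emergent as starting after first treatment. A non-treatment-emergent listing would naturally hold screening events, which 12.1 says are not AEs. Read literally, it could still hold events that start during the first application.

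**Scale**

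- Screening is 4 weeks and participation about 14 weeks (Section 3): 4 / 14 = 28.6% of planned time lies outside the AE window.
- With 148 subjects, 148 × 4 = 592 subject-weeks. Section 11.3.1 calls the 148 enrolled, and 11.3.5 calls them randomized. If they are randomized, screening time of screen failures comes on top. If they are enrolled at consent, screen failures are already among the 148.
- This measures time, not risk. Without a background rate in the documents, no expected number of unreported SAEs can be computed.

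**The case against.** A reader might infer that every serious screening event goes unreported and leaves no trace. The documents do not support that.

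- The screening diary records changes in health (11.1.1), and the investigator reviews them at Visit 1 (11.5.2).
- A pCRF is due for every subject who signed consent (14.2). Reasons, circumstances and findings at early withdrawal go on the End of Study page (11.3.4, 11.5.4).
- SAP 4.2 lists relevant medical history, and SAP 4.8 covers untreated subjects in discontinuation outputs.
- Worsening after first use is an AE, and the undated hospitalization sentence may reach some migraine admissions.

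The likely frequency is also low. Screening consists of history, physical examination, a urine pregnancy test, questionnaires and a diary (11.5.1), with a SARS-CoV-2 test before treatment at Visit 1 where site policy requires it. Section 8.3 describes the mandated measures other than the device as carrying virtually no added risk. The prophylaxis requirement continues a regimen already stable for 3 months, and 11.2.5 lets the investigator give medication needed for safety and well-being at any time.

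All of this stands, and it limits the size of the point. It does not close the gap. A medical-history entry triggers no 24-hour report and no causality assessment, and none of these passages states when SAE collection begins.

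It can also be argued that the conflict concerns only events related to procedures or trial conditions, so collecting all serious events goes too far. But the relation is known only after an assessment, and the protocol provides that assessment only for AEs. Section 12.4 already asks sites to report SAEs whatever their cause.

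**Conclusion.** The concern holds in this form: the protocol places all events between consent and first device use outside the AE definition, so it sets no clear duty to classify, assess or expedite a serious one. Other parts of the protocol and SAP assume that such a duty or such records exist. The gap lies in SAE classification and expedited reporting, not in all documentation.

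It covers about 28.6% of each completing subject's planned time. The number of events affected is probably small and cannot be calculated from the documents. The primary endpoint, the error rate and the treatment-emergent tables are unaffected. The change is still worth making, because a site following the rule as written could leave a trial-related serious event outside expedited reporting.

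The conclusion rests on reading the SAE definition as nested within the AE definition, which is what 12.1 says. On the outputs for untreated subjects it rests on the body of the SAP; the detailed output list in Appendix A was not available for this review and may say more.

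**What to change.** In the protocol, reconcile 12.1, 12.2.1, 12.5, 11.4.1 and schedule footnote a with 12.4, and state the start of SAE collection explicitly:

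- From signature of consent, any event meeting a seriousness criterion in 12.1 is recorded as an AE, assessed for relation to CIP procedures and to the conditions of the trial, and reported under 12.4, whether or not the subject is later treated.
- Non-serious events before first treatment remain medical history.
- Section 12.5 includes consented but untreated subjects for these serious events.
- Section 11.4.1 and the schedule agree on when the diary starts to collect AEs.

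In SAP 4.4, place these events in the non-treatment-emergent listing. In SAP 4.8, include screened-but-untreated subjects in that listing. The definition of treatment-emergent AEs stays as it is.

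The SAP reports that the interim analysis has already taken place, so expedited reporting can change only for subjects still to be screened. For those already screened, medical history and End of Study pages can be checked for qualifying events.

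The cost is a wording amendment with its usual submissions, a small SAP edit and a few extra SAE forms.
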